8.2 Specification of Safety Parameters

Safety will be assessed by the frequency and severity of:

- Occurrence of SAEs from the administration of AV-1 to final follow-up visit on Day 120 (±5).
- Occurrence of unsolicited AEs from the administration of AV-1 to the final follow-up visit on Day 120 (±5).
- Occurrence of solicited AEs from the administration of AV-1 to Day 8.

- Occurrence of changes from baseline in physical examination, vital sign measurements, and clinical safety laboratory values from the administration of AV-1 to the final follow-up visit on Day 120 (±5).
- Occurrence of changes from baseline in ECG parameters in the 48 hours after starting the AV-1 infusion and at Days 8 (+2), 43 (\pm 3), 85 (\pm 5), and 120 (\pm 5).

8.2.1 Solicited and Unsolicited Events

Solicited events are AEs that are common and known to occur following administration of the IP. Solicited events are defined in Table 17-1.

Unsolicited events are any other AEs that occur following administration of the IP.

8.2.2 Dose Escalation Criteria

This study is designed such that dose escalation is allowed only after a blinded safety data review of each cohort by the SRC has occurred as outlined in Section 8.7.1. Study assessments (eg, AEs, clinical laboratory test results, vital sign measurements, and 12-lead ECG results) will be used to evaluate safety of a given dose level. Dose escalation will be dependent on review of the safety data. Clinically significant results will be discussed with the Sponsor before dose escalation continues. Data from a minimum of 6 subjects dosed per cohort must be reviewed before each dose escalation.

Based on the review of safety data and recommendations by the SRC, SMC, or both, the Sponsor and the Investigator may choose to repeat a dose level, administer a dose less than the previous dose, escalate to a dose lower than the next planned dose, or prolong the duration of the infusion. Before implementing any change, the IRB will be notified and provided with the rationale for approval.

8.2.3 Sentinel Subjects

As a safety precaution in this first-in-human study, each cohort is divided into 2 groups with each group being dosed at least 72 hours apart. On the first day of dosing in all cohorts, the first group in each cohort will be comprised of 2 sentinel subjects. The randomization schedule will be constructed such that one of the sentinel subjects dosed on the first day will be randomly assigned to receive AV-1 and one of the sentinel subjects will be randomly assigned to receive placebo. After Investigator review of the safety data from the 48-hour postdose period for the sentinel subjects, which includes review of any AEs, abnormalities in ECGs, safety laboratory assessments, and vital signs, the remainder of the cohort (5 subjects randomly assigned to AV-1; one subject randomly assigned to placebo) will be dosed at least 72 hours after the sentinel subjects. Continuation from the sentinel subjects to dose the remaining 6 subjects will proceed if no study halting criteria are met as outlined in Section 8.6.3.

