Sentinel dosing will be used in each cohort as discussed in Section 8.2.3. In each cohort, the Investigator will review safety data for the sentinel subjects and notify the Sponsor of intent to proceed with dosing the rest of the cohort with a minimum of 72 hours between dosing of the sentinel subjects and dosing the rest of the cohort. Safety data through Day 8 will be reviewed in a blinded fashion by the safety review committee (SRC) (Section 8.7.1) for each dose cohort before escalating to the next dose cohort (Section 8.2.2). Based on the review of safety and PK data, the Sponsor and the Investigator may choose to repeat a dose level, administer a dose less than the previous dose, escalate to a dose lower than the next planned dose, or prolong the duration of the infusion.

On Day 5, subjects will be discharged after all protocol-specified assessments have been completed. Subjects will return for 8 follow-up visits on Days 8 (+2), 15 (\pm 2), 22 (\pm 2), 29 (\pm 2), 43 (\pm 3), 57 (\pm 3), 85 (\pm 5), and 120 (\pm 5). Subjects will be asked to attend an early termination

(ET) visit if they withdraw or are withdrawn from the study prior to the final follow-up visit on Day $120 (\pm 5)$.

Safety, PK, and anti-AV-1 antibody endpoints will be evaluated in the study. Clinical laboratory evaluations, physical examination findings, vital sign measurements, safety 12-lead electrocardiograms (ECGs), incidence and severity of AEs, and incidence of serious AEs (SAEs) will be monitored to assess safety (Section 7 and Section 8).

Blood samples for PK analysis of AV-1 will be collected predose (within 15 minutes); at 0.5, 1 (end of infusion), 1.25, 1.5, 2, 3, 4, 6, 8, 12, 24, and 48 hours after the start of infusion; Day 5 prior to discharge; and at the follow-up visits on Days 8 (+2), 15 (\pm 2), 22 (\pm 2), 29 (\pm 2), 43 (\pm 3), 57 (\pm 3), 85 (\pm 5), and 120 (\pm 5) (or ET) (Section 7.2.2).

Blood samples for anti-AV-1 antibody analysis will be collected on Day -1 and on Days 29 (± 2) 85 (± 5), and 120 (± 5) (or ET) to evaluate for the presence of pre-existing or treatment-emergent anti-AV-1 antibodies.

A blood sample will be collected at baseline for hypersensitivity testing and additional samples will be collected if a suspected hypersensitivity reaction or anaphylactic response occurs (Section 7.2.4).

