8.6 Halting Rules

8.6.1 Dose Escalation Halting Criteria

If either of the following criteria is met, escalation to the next planned dose cohort will not proceed until all available study data have been reviewed by the SMC.

- Two or more subjects in the same cohort experience a Grade 2 related AE (laboratory or systemic) that is attributed to the study drug and coded under the same high-level term per the Medical Dictionary for Regulatory Activities coding, throughout the duration of the study.
- Two or more subjects in the same cohort experience a Grade 3 AE (laboratory or systemic) that is coded under the same high-level term per the Medical Dictionary for Regulatory Activities coding, regardless of causality assessment by the Investigator, throughout the duration of the study.

If dose escalation is halted, the study may resume if deemed acceptable by the SMC following review of all available study data.

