8.6.2 Halting Criteria for Subject Infusions

The Investigator and study site staff must carefully observe the subjects for any AE during the infusion.

The infusion will be halted for an individual subject and will not resume if any of the following manifestations occur during the 1-hour infusion:

- Occurrence during dosing that, in the opinion of the Investigator, results in the inability to have confidence that the intended dose of IP was delivered.
- Infusion-related reaction of Grade 2 or higher.

In case of a suspected infusion-related reaction, at the discretion of the Investigator, the infusion rate may be slowed from a rate of 250 mL/hour to a rate of 125 mL/hour for symptom management. The infusion may also be stopped. The subject will be observed to determine the severity of the reaction for a period of up to 15 minutes. Depending on the assessment of the subject, supportive care can be administered, and the infusion may permanently be stopped. If the Investigator determines that there is no infusion reaction, no ongoing supportive care is required after dosing is stopped, or if the symptoms of the clinical reaction have been improved after 15 minutes, the infusion may be restarted. The decision to

continue the infusion is based on the assessment by the Investigator. The infusion will be halted if there is a reoccurrence after a pause in dosing.

- Symptomatic low blood pressure of <90 mm Hg systolic or >30% decrease from baseline in systolic or diastolic blood pressure at predose.
- Confirmed tachycardia with an increase in resting heat rate to ≥130 beats per minute (bpm), or development of ventricular dysrhythmia, or bradycardia (<45 bpm, or <40 bpm in subjects with baseline of <60 bpm) associated with complaints of dizziness, nausea, or feeling faint.
- Syncope.
- Confusion.
- Suspected Grade 3 AE or SAE.

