8.6.3 Study Halting Criteria

Study dosing must be stopped, and a review of available safety data will be conducted by the SMC if any of the following occur:

- Death of a dosed subject following infusion and prior to the subject's last follow-up visit that was not the result of trauma or accident, regardless of relatedness to the IP.
- Occurrence of a life-threatening allergic/hypersensitivity reaction (eg, anaphylaxis) in any subject, manifested by bronchospasm with or without urticaria, or angioedema requiring hemodynamic support with pressor medications or mechanical ventilation.
- One subject with an IP-related SAE of any grade.
- Two or more subjects with a Grade 3 AE in the same system organ class (systemic toxicity, clinical laboratory tests, or vital sign measurements) considered related to the IP, except scenarios where there are acceptable physiological explanations for a Grade 3 abnormality (eg, Grade 3 hematuria in a menstruating female).
- One or more subjects experience a confirmed Grade 3 QTcF (≥500 msec or increase ≥60 msec), or 2 or more subjects cumulatively have experienced a Grade 2 change in QTcF (≥480 msec).

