8.7 Safety Oversight

8.7.1 Safety Review Committee

The SRC is composed of the DMID Medical Monitor, Sponsor Medical Monitor, and the Investigator at the clinical site. Objective dose escalation criteria and safety evaluations will be utilized. The Investigator will evaluate safety data from the sentinel group and notify the Sponsor Representative of intent to proceed if no study halting criteria (Section 8.6.3) are met. The SRC will evaluate the safety data through Day 8 for each cohort to determine whether dose escalation

can occur. These reviews do not necessitate formal meetings. The SRC will inform the Sponsor Representative that the study can proceed to begin dosing the next cohort if none of the events described in the study halting criteria (Section 8.6.3) or dose escalation criteria (Section 8.2.2) are met.

Should any of the study halting criteria or dose escalation halting criteria be met, the SMC will meet to evaluate the data and recommend appropriateness of further dosing. The decision to advance to the next dosing cohort will be documented and provided to the SRC and Sponsor Representative.

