10.3 Treatment Assignment Procedures

The PPD randomization statistician will generate the randomization schedule. The PPD randomization statistician will not directly be involved in study conduct, data management, or data analysis. The first group will be comprised of 2 eligible subjects (sentinel subjects), with 1 subject randomly assigned to receive AV-1 and 1 subject randomly assigned to receive placebo. The second group will be comprised of 6 eligible subjects (remaining cohort), with 5 subjects randomly assigned to receive AV-1 and 1 subject randomly assigned to receive placebo with an overall ratio of 6:2 in each cohort. Continuation to dose the remaining 6 subjects in the second group will be at the discretion of the Investigator following consultation with the Sponsor Representative.

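### The sentinel release rule is worded two ways, and no text requires a hold after a sentinel's first related, non-serious, non-QTcF Grade 3 AE or a permanent safety stop of the infusion

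*Protocol*

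**What the plan says.** Protocol 8.2.3 splits each cohort into two sentinels (one AV-1, one placebo) and a second group of six (five AV-1, one placebo), dosed at least 72 hours later. The Investigator reviews the sentinels' 48-hour AEs, ECGs, laboratory results and vital signs. The rule for going on is: "Continuation from the sentinel subjects to dose the remaining 6 subjects will proceed if no study halting criteria are met".

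Section 8.7.1 has the Investigator "notify the Sponsor Representative of intent to proceed if no study halting criteria (Section 8.6.3) are met". Section 10.3 describes the same step differently: dosing the second group "will be at the discretion of the Investigator following consultation with the Sponsor Representative". It cites no criterion. Section 3.1 gives no criterion either, but refers back: "Sentinel dosing will be used in each cohort as discussed in Section 8.2.3".

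Three sets of halting rules could bear on this step:

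- **8.6.3 (study dosing).** One subject is enough for non-accidental death, life-threatening hypersensitivity, a related SAE or a confirmed Grade 3 QTcF. Other Grade 3 AEs, if related, need "Two or more subjects with a Grade 3 AE in the same system organ class", "except scenarios where there are acceptable physiological explanations for a Grade 3 abnormality". Two subjects with a Grade 2 QTcF change also count.
- **8.6.1 (escalation).** It needs two subjects in the same cohort, and its consequence is that "escalation to the next planned dose cohort will not proceed until all available study data have been reviewed by the SMC".
- **8.6.2 (one subject's infusion).** "The infusion will be halted for an individual subject and will not resume if any of the following manifestations occur". The list includes a Grade 2 infusion-related reaction, symptomatic hypotension, syncope, confusion and a suspected Grade 3 AE.

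**The concern.** Section 2.3.1 relies on sentinel dosing to limit the harm from unforeseen drug effects in a first-in-human trial. That works best if a worrying event in the one sentinel on active drug reliably pauses the cohort. Here the release test is borrowed from the study-wide halting criteria, whose general Grade 3 rule counts to two subjects, while the gate looks at one AV-1 subject.

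The sections also disagree on who decides and how. Notifying the Sponsor Representative of an intent to proceed is not the same as consulting before a discretionary decision. A site following 8.2.3 and 8.7.1 and a site following 10.3 could act differently on the same data.

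At stake each time is the exposure of five more healthy volunteers to the same new dose, decided at a gate where the SRC has no stated role.

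**Working it through.** **1. Group sizes.** From 8.2.3 and 10.3: (1 + 1) + (5 + 1) = 8 per cohort, of whom 1 + 5 = 6 receive AV-1 and 1 + 1 = 2 placebo. Five cohorts give 5 × 8 = 40, which matches 10.2. AV-1 subjects dosed after a sentinel gate number 5 × 5 = 25 of 5 × 6 = 30.

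**2. Two sentinel events run through each rule.** Event A is a first related, non-serious, non-QTcF Grade 3 AE, meaning one that is not the second related Grade 3 AE in its system organ class across the study. Event B is a permanent 8.6.2 safety stop that is not itself an 8.6.3 event.

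| Text | Event A | Event B |
|---|---|---|
| 8.6.3 | Count 1, threshold 2: no halt | No criterion met: no halt |
| 8.6.1 | Count 1, threshold 2; governs the next cohort only | Same |
| 8.6.2 | Acts on that subject's infusion only | Acts on that subject's infusion only |
| 8.5 | Immediate repeat of a Grade 3 finding; no hold | No hold |
| 5.2.1, 5.2.2, Section 6 | Silent on the second group | Subject may be stopped and replaced; infusion documented; silent on the second group |
| 8.2.2 | Sponsor discussion tied to escalation | Same |
| 8.7.2 | Safety monitoring committee (SMC) review only if a criterion is met, an SAE occurs or the Sponsor asks | Same |
| 10.3, 10.3.3 | Investigator may decline; unblinding possible; neither obligatory | Same |

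Examples of A, if not judged an important medical event under 8.1.2: generalized urticaria that is not life-threatening (Table 17-1), or an asymptomatic ALT above 5 × ULN on the 48-hour sample (Table 17-3). Examples of B: a stop for a Grade 2 infusion reaction, syncope or confusion.

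**3. When the two-subject Grade 3 rule can fire before release.** In Cohort 1 only the two sentinels have been dosed, so reaching two requires the placebo sentinel to have a related Grade 3 AE in the same class. In Cohorts 2 to 5 an earlier subject's event can complete the count, reading 8.6.3 as study-wide because, unlike 8.6.1, it states no cohort limit.

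**4. Both sentinels affected.** If both sentinels met an 8.6.1 criterion, 8.7.1 would have the SMC advise on further dosing. This again needs two events, one in the placebo sentinel, and 8.6.1 itself blocks only the next cohort.

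**5. What an early stop leaves untested.** Assuming dose delivered is proportional to volume delivered, the AV-1 sentinel has received less than the previous cohort's full dose if the stop comes before the fraction (previous dose / current dose):

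- 90 mg: 30/90 = 33.3%
- 250 mg: 90/250 = 36.0%
- 500 mg: 250/500 = 50%
- 1000 mg: 500/1000 = 50%

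In Cohort 1, any early stop of the AV-1 sentinel means nobody has yet received the full 30 mg.

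**The case against.** The strongest reply is that the sections can be reconciled. On that reading, 8.2.3 and 8.7.1 bar release when an 8.6.3 criterion is met, and 10.3 adds discretion and consultation on top. Below the single-subject triggers the protocol deliberately relies on medical judgement, supported by a compulsory 48-hour review, a 72-hour gap and, under 8.5, laboratory review within 24 hours of receipt with immediate repeat of Grade 3 findings. The nonclinical background is clean, with a stated margin above 90-fold at the starting dose and about 3-fold at the top dose.

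Much of this stands. The safeguards are real, and the reconciled reading is sensible. But 8.2.3 states a positive rule for proceeding, and the reader has to supply the reconciliation. Even when reconciled, the text makes every hold in events A and B optional.

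Three stronger readings are tempting and are not supported:

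- **That sentinels go unreviewed, or that the site is compelled to dose on.** Review is mandatory, and 10.3 lets the Investigator decline.
- **That the gap can be priced as expected further events among the five.** The documents give no event rate. Any such figure would also not measure events averted, because dosing may resume after a hold.
- **That every incomplete sentinel infusion must be replaced.** Section 5.2.2 leaves replacement to discretion, and interrupted saline in a placebo sentinel says nothing about the new dose.

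**Conclusion.** The point holds as a gap in a safety rule that should be closed; it is not an error in the trial's logic. The go-ahead is worded in two ways. In addition, the general Grade 3 trigger needs two subjects at a gate with one AV-1 sentinel, so it is nearly inoperative there. After event A or event B, five more AV-1 subjects could be dosed in that cohort with no section breached, and the same structure recurs in all five cohorts.

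This rests on the wording alone, plus the study-wide reading of the two-subject rule in 8.6.3. A cohort-only reading would make that trigger weaker still at the gate in Cohorts 2 to 5. No event rate is needed. What is missing is an obligation to pause, not a review.

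**What to change.** In 8.2.3, 8.7.1 and 10.3, state one rule: absence of an 8.6.3 criterion is necessary but not sufficient for release, and the Investigator decides after consulting the Sponsor Representative.

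Then add:

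- **Hold.** The second group waits for blinded SRC review if either sentinel (a) has a related Grade 3 AE, confirmed on the 8.5 repeat if it is a laboratory value and keeping the 8.6.3 physiological exception, or (b) has the infusion permanently stopped for a safety reason under 8.6.2. Applying this to either sentinel keeps the blind.
- **Referral.** The SRC refers to the SMC if an 8.6.3 criterion is met, or if the SRC or Sponsor asks.
- **Incomplete infusion.** If a sentinel did not receive the full infusion, the SRC considers, at its discretion and under 5.2.2, whether a replacement sentinel with the same assignment should be dosed first.

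The cost is a wording amendment with IRB approval (9.1) and an occasional short delay; SRC reviews need no formal meeting (8.7.1). Frequency has to be assumed. If the chance of a hold is h per cohort, expected holds over the trial are 5h: 5 × 0.01 = 0.05, 5 × 0.10 = 0.5 and 5 × 0.30 = 1.5. A replacement sentinel, if chosen, would use one of the eight replacement places in 10.2 and, with the usual interval, add at least 72 hours.

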8.3 Reporting Procedures

8.3.1 Reporting Serious Adverse Events

[figure not shown]
Serious AEs will be followed until resolution even if this extends beyond the study-reporting period. Resolution of an AE is defined as the return to pretreatment status or stabilization of the condition with the expectation that it will remain chronic.

Any AE that meets a protocol-defined serious criterion must be submitted immediately (within 24 hours of site awareness) on an SAE form to:

PPD PVG Safety:	
Telephone (24 hour):	
Fax:	
Email:	

PPD PVG Safety will notify and submit to the DMID Pharmacovigilance Group within 1 business day to:

DMID Pharmacovigilance Group
Clinical Research Operations and Management Support

In addition to the SAE form, select SAE data fields must also be entered into the Electronic Data Capture system.

Other supporting documentation of the event may be requested by the Sponsor Representative or DMID Pharmacovigilance Group and should be provided as specified in the safety management plan.

The Sponsor's Representative, Sponsor's Medical Monitor, and DMID Clinical Project Manager will also be notified of the SAE by the PPD Pharmacovigilance Group within 1 business day and will review and assess the SAE for regulatory reporting and potential impact on study subject safety and protocol conduct.

At any time after completion of the study, if the Investigator or subinvestigator becomes aware of an SAE that is suspected to be related to the IP, the Investigator or subinvestigator will report the event to the Sponsor Representative and DMID Pharmacovigilance Group.

8.3.2 Regulatory Reporting

Following notification from the Investigator, PPD will report events that are both serious and unexpected that are related to the IP to the FDA on behalf of AbViro, LLC (the Sponsor) and

within the required timelines as specified in 21 CFR Part 312.32: fatal and life-threatening events within 7 calendar days (by telephone or fax). All written reports will be sent to the FDA within 15 calendar days. All SAEs designated as "not related" to the IP, will be reported to the FDA at least annually in a summary format.

8.3.3 Reporting of Pregnancy

Subjects will be instructed that if they or their partner becomes pregnant during the study, this should be reported to the Investigator. The Investigator should also be notified of a pregnancy occurring during the study but confirmed after completion of the study. In the event that a subject or a subject's partner is subsequently found to be pregnant after the subject is enrolled in the study and has received the IP, the pregnancy will be followed through its resolution, and the status of the mother and child will be reported to the Sponsor after delivery.

A pregnancy notification form and follow-up will be completed.

8.4 Type and Duration of Follow-up of Subjects after Adverse Events

Adverse events will be assessed and followed from initial recognition of the AE through resolution even if the duration of follow-up goes beyond the final follow-up visit.

Serious AEs will be followed through resolution even if duration of follow-up goes beyond the final follow-up visit.

Resolution of an AE is defined as the return to pretreatment status or stabilization of the condition with the expectation that it will remain chronic.

8.5 Procedures to be Followed in the Event of Abnormal Laboratory Test Values or Abnormal Clinical Findings

Results of laboratory values collected during the conduct of the study will be reviewed by the Investigator or designee within 24 hours of receipt at the clinical site. As this study will be conducted in healthy subjects, assessment of laboratory abnormalities will be performed in accordance with the grading scale provided in Section 17.2, which is adapted from the FDA guideline, "Toxicity Grading Scale for Healthy Adult and Adolescent Volunteers Enrolled in Preventive Vaccine Clinical Trials" (DHHS 2007). The adaptation is applied to account for local laboratory normal values and for compliance with the Clinical Data Interchange Standards Consortium. Any findings meeting Grade 3 criteria must be repeated immediately to rule out spurious values. All abnormal laboratory test values and findings on physical examination will be included in the study data and summarized in the safety analyses as described in Section 10.4.5. Any treatment-emergent AEs that are appropriately graded according to the toxicity scale in Section 17.2 will be captured as AEs in the eCRF.

Abnormal laboratory values occurring during the study will be followed until repeat test results return to normal, stabilize, or a cause is identified. If the laboratory abnormality is identified at the final scheduled visit, the subject will be requested to return for additional testing.

